6.6.2.4 Management of Hepatotoxicity

Liver function tests (ALT, AST, bilirubin levels) should be conducted as detailed in the SoA (Section 1.3.1 and Section 1.3.3) and as clinically indicated. If signs/symptoms indicating liver injury occur, instructions contained in [Table 8](#) should be followed. Appropriate supportive care should be provided together with close monitoring. If hepatic failure occurs, the study drug must be discontinued. If hepatic failure (any grade per CTCAE v5) occurs, lenvatinib must be discontinued.

6.6.2.5 Management of Thromboembolic Events

Participants should be advised to pay attention to symptoms suggestive of venous thromboembolic events which include acute onset of shortness of breath, dyspnea, chest pain, cough, hemoptysis, tachypnea, tachycardia, cyanosis, DVT signs including lower-extremity swelling, and warmth to touch or tenderness. In case any of these symptoms appear, participants should be instructed to report such symptoms promptly to the treating physician. If a thromboembolic event is confirmed, instructions contained in [Table 8](#) should be followed. Appropriate supportive care should be provided together with close monitoring. If a participant experiences a Grade 3 or a life-threatening (Grade 4) thromboembolic reaction, including pulmonary embolism, lenvatinib must be discontinued.

Arterial thromboembolic events (eg, new onset, worsening, or unstable angina, myocardial infarction, transient ischemic attack, and cerebrovascular accident) of any grade require study treatment discontinuation.

6.6.2.6 Management of Posterior Reversible Encephalopathy Syndrome/Reversible Encephalopathy Syndrome/ Reversible Posterior Leukoencephalopathy Syndrome

Posterior Reversible Encephalopathy Syndrome/Reversible Encephalopathy Syndrome/ Reversible Posterior Leukoencephalopathy Syndrome (PRES/RPLS) is a neurological disorder that can present with headache, seizure, lethargy, confusion, altered mental function, blindness, and other visual or neurological disturbances. Mild to severe hypertension may be present. MRI is necessary to confirm the diagnosis of PRES/RPLS. Appropriate measures

should be taken to control BP. In participants with signs or symptoms of PRES/RPLS, instructions in [Table 8](#) should be followed.

6.6.2.7 Management of Hypocalcemia

Serum calcium should be monitored per the SoA (Section 1.3.1 and Section 1.3.3). Corrected serum calcium should be used to assess the grade of hypocalcemia per CTCAE v5.0, using the following formula:

$$\text{Corrected calcium} = ([4 - \text{serum albumin in g/dL}] \times 0.8 + \text{serum calcium})$$

The formula is not applicable when serum albumin concentration is normal (>4 g/dL); in such situations, the total (uncorrected) serum calcium should be used instead.

Hypocalcemia should be treated per institutional guidelines (eg, using appropriate calcium, magnesium, and Vitamin D supplementation) until resolution.

6.6.2.8 Management of Hemorrhage

Instructions in [Table 8](#) should be followed for the management of hemorrhage. Either resume at a reduced dose or discontinue lenvatinib depending on the severity and persistence of hemorrhage.

6.6.2.9 Management of Gastrointestinal Perforation or Fistula Formation

Lenvatinib should be discontinued in any participants who develop gastrointestinal perforation of any grade or Grade 4 fistula. Refer to Appendix 7 for country-specific requirements.

6.6.2.10 Management of QT Prolongation

Lenvatinib should be withheld in the event of development of QT interval prolongation greater than 500 msec. Lenvatinib should be resumed at a reduced dose when QTc prolongation is resolved to <480 msec or baseline. Monitor potassium, calcium and magnesium and replenish as appropriate.

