5.2 Exclusion Criteria

The participant must be excluded from the study if the participant:

Medical Conditions

- Has collecting duct histology.
- A WOCBP who has a positive urine pregnancy test within 24 hours before the first dose of study intervention (see Appendix 2 and Appendix 5). If the urine test cannot be confirmed as negative, a serum pregnancy test is required. In such cases, the participant must be excluded from participation if the serum pregnancy result is positive.
- Has pre-existing \geq Grade 3 gastrointestinal or non-gastrointestinal fistula.

4. Has urine protein ≥ 1 g/24 hours.
Note: Participants with proteinuria $\geq 2+$ (≥ 100 mg/dL) on urine dipstick testing (urinalysis) will undergo 24-hour urine collection for quantitative assessment of proteinuria.
5. Has a left ventricular ejection fraction below the institutional (or local laboratory) normal range, as determined by multigated acquisition or echocardiogram.
6. Has radiographic encasement or invasion of a major blood vessel, or of intratumoral cavitation.

Note: the degree of proximity to major blood vessels should be considered because of the potential risk of severe hemorrhage associated with tumor shrinkage/necrosis following lenvatinib therapy.
7. Has prolongation of QTcF interval to >480 msec.
8. Has clinically significant cardiovascular disease within 12 months from first dose of study intervention, including New York Heart Association Class III or IV congestive heart failure, unstable angina, myocardial infarction, cerebral vascular accident, or cardiac arrhythmia associated with hemodynamic instability. Note: Medically controlled arrhythmia would be permitted.
9. Has gastrointestinal malabsorption, gastrointestinal anastomosis, or any other condition that might affect the absorption of lenvatinib.
10. Has active hemoptysis (bright red blood of at least 0.5 teaspoon) within 3 weeks prior to the first dose of study drug.

Prior/Concomitant Therapy

11. Has had major surgery within 3 weeks prior to first dose of study intervention. Note: Adequate wound healing after major surgery must be assessed clinically, independent of time elapsed for eligibility.
12. Has received prior therapy with an anti-PD-1, anti-PD-L1, or anti-PD-L2 agent or with an agent directed to another stimulatory or co-inhibitory T-cell receptor (eg, CTLA-4, OX-40, CD137).
13. Has received prior systemic anticancer therapy including investigational agents within 4 weeks prior to allocation.

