6.6.2 Dose Modification With Lenvatinib

Lenvatinib dose reduction and interruption for participants who experience pembrolizumab + lenvatinib combination therapy-related toxicity will be in accordance with the dose modification guidelines described in Table 8. An interruption of lenvatinib for more than 28 days will require Sponsor approval before treatment can be resumed.

The starting dose of lenvatinib is 20 mg/day. Dose reductions of lenvatinib occur in succession based on the previous dose level (14, 10, 8 mg/day). Any dose reduction below 8 mg/day must be discussed with the Sponsor. Once the lenvatinib dose has been reduced, it

may not be increased at a later date, unless the dose has been mistakenly decreased; in this situation, the Sponsor's approval is required to increase the dose.

Refer to the subsections below for management of hypertension (Section 6.6.2.1), proteinuria (Section 6.6.2.2), diarrhea (Section 6.6.2.3), hepatotoxicity (Section 6.6.2.4), thromboembolic events (Section 6.6.2.5), posterior reversible encephalopathy syndrome/ reversible posterior leukoencephalopathy syndrome (PRES/RPLS; Section 6.6.2.6), hypocalcemia (Section 6.6.2.7), hemorrhage (Section 6.6.2.8), gastrointestinal perforation or fistula formation (Section 6.6.2.9), QT prolongation (Section 6.6.2.10), and ONJ (Section 6.6.2.11) as appropriate, before consulting the dose modification table (Table 8). For overlapping toxicities of pembrolizumab and lenvatinib, please refer to Section 6.6.3.

Table 8 Dose Modification Guidelines for Lenvatinib-Related Adverse Events

Treatment-Related Toxicity ^{a,b}	Management	Dose Adjustment
Grade 1 or Tolerable Grade 2		
	Continue treatment	No change
Intolerable Grade 2^{c,d} or Grade 3^{e,f}		
First occurrence	Interrupt lenvatinib until resolved to Grade 0-1, or tolerable Grade 2	Reduce lenvatinib dose to 14 mg once a day (1-level reduction)
Second occurrence (same toxicity or new toxicity)	Interrupt lenvatinib until resolved to Grade 0-1, or tolerable Grade 2	Reduce lenvatinib dose to 10 mg once a day (1-level reduction)
Third occurrence (same toxicity or new toxicity)	Interrupt lenvatinib until resolved to Grade 0-1, or tolerable Grade 2	Reduce lenvatinib dose to 8 mg orally once a day (1-level reduction)
Fourth occurrence (same toxicity or new toxicity)	Interrupt lenvatinib	Discuss with Sponsor
Grade 4^g: Discontinue Study Treatment		

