8.3.3 Electrocardiograms

ECGs will be obtained as designated in the SoA (Section 1.3). Complete, standardized, 12-lead ECG recordings that permit all 12 leads to be displayed on a single page with an accompanying lead II rhythm strip below the customary 3×4 lead format are to be used. In addition to a rhythm strip, a minimum of 3 full complexes should be recorded from each lead simultaneously. Participants must be in the recumbent position for a period of 5 minutes prior to the ECG. The QTcF correction method for calculating QTc will be used.

An ECG abnormality may meet the criteria of an AE as described in this protocol (see Appendix 3) and the CRF Completion Guidelines. In these instances, the AE corresponding to the ECG abnormality will be recorded on the appropriate CRF.

QTc prolongation has been seen in some lenvatinib studies. For participants receiving lenvatinib, ECGs will be monitored at every cycle (as specified in the SoA in Section 1.3) in participants with congenital long QT syndrome, congestive heart failure, bradyarrhythmias, or those who are taking drugs known to prolong the QT interval, including Class Ia and III antiarrhythmics. Medicinal products with a known potential to prolong the QT/QTc interval must be used cautiously. Please refer to the lenvatinib prescribing information for further details.

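### Section 6.6.2.10 sets the lenvatinib hold on uncorrected QT but the resume rule on QTc; both should name QTcF

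*Combined protocol and SAP*

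**What the plan says.** Section 6.6.2.10 gives two numeric rules in consecutive sentences.

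- Hold: "Lenvatinib should be withheld in the event of development of QT interval prolongation greater than 500 msec".
- Resume: "Lenvatinib should be resumed at a reduced dose when QTc prolongation is resolved to <480 msec or baseline".

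The first names no correction. The second is on QTc, without a formula. The formula comes from Section 8.3.3: "The QTcF correction method for calculating QTc will be used". The same section describes the risk on the corrected scale: "QTc prolongation has been seen in some lenvatinib studies". Exclusion criterion 7 in Section 5.2 is on that scale too: "Has prolongation of QTcF interval to >480 msec".

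Section 6.6.2 sets the lenvatinib dose steps at 20, 14, 10 and 8 mg/day. A reduced dose may be raised again only if the reduction was made in error and the Sponsor approves. Nowhere do the documents say that the QT interval in the hold rule means corrected QT.

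**The concern.** A hold rule and its matching resume rule should be on one scale. Here the words put them on two, and the method statement in Section 8.3.3 covers QTc, so by its terms it does not reach a rule written for the QT interval. The gap between raw QT and QTcF depends on heart rate, so the literal rule errs in both directions.

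At faster rates, a participant with QTcF above 500 msec could fail to meet the hold. After Cycle 2, Table 1 schedules ECGs every other 42-day cycle, so the next scheduled ECG could be 2 × 42 = 84 days (12 weeks) later, or 6 weeks later in high-risk participants.

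At slow rates, a participant could be held without need and then restarted at a lower dose. Slow rates are foreseeable: the group that Section 8.3.3 singles out for ECGs every cycle includes "participants with congenital long QT syndrome, congestive heart failure, bradyarrhythmias".

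**Working it through.** The plan states no figure to reproduce. The check is a comparison of the text followed by a conversion between scales.

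**Which scale each rule uses**

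| Place | Measure named | Limit |
|---|---|---|
| Exclusion criterion 7 (5.2) | QTcF | >480 msec |
| Hold (6.6.2.10) | QT interval, no correction | >500 msec |
| Resume (6.6.2.10) | QTc, which 8.3.3 makes QTcF | <480 msec or baseline |

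Only the hold is off the QTcF scale.

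**Conversion.** The Fridericia formula is QTcF = QT / (60/HR)^(1/3), with HR in beats per minute. The 500 and 480 msec limits are from Section 6.6.2.10. The heart rates are assumed for illustration.

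At 80 bpm, (60/80)^(1/3) = 0.9086, so a raw QT of 500 msec is 500/0.9086 = 550.3 msec. The other rows follow in the same way.

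| Heart rate (bpm) | QTcF when raw QT = 500 msec | Difference from 500 |
|---|---|---|
| 45 | 454.3 | −45.7 |
| 50 | 470.5 | −29.5 |
| 53 | 479.7 | −20.3 |
| 57 | 491.5 | −8.5 |
| 60 | 500.0 | 0 |
| 63 | 508.2 | +8.2 |
| 70 | 526.4 | +26.4 |
| 80 | 550.3 | +50.3 |

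**Late hold.** Above 60 bpm the literal rule fires only at a QTcF above 500 msec. At 80 bpm, a participant with QTcF anywhere from 501 to 550 msec would not be held under this section.

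**Needless hold.** Set a raw QT of 500 msec equal to a QTcF of 480 msec and solve for heart rate: HR = 60/(500/480)^3 = 53.1 bpm. Below that rate, a raw QT just over 500 msec triggers the hold while QTcF is already under the resume limit, so one ECG can satisfy both rules. The first dose step at restart is (20 − 14)/20 = 30%.

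**With QTcF in both sentences.** Hold and resume are 500 − 480 = 20 msec apart at every heart rate. The raw QT matching a QTcF of 500 msec is then 531.3 msec at 50 bpm, 500.0 at 60 and 454.3 at 80.

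**The case against.** The strongest reply is that the context settles the meaning. The resume sentence speaks of QTc prolongation having resolved, and what resolves is what triggered the hold. Section 8.3.3 describes the risk as QTc prolongation, and nothing tells a site to act on raw QT. On this view the defect is one missing letter, the resume sentence already means QTcF, and the harm depends on a reading that few sites would adopt. This largely stands as to intent, and the real gap is indeed in the hold sentence. It does not excuse leaving a drug-hold threshold to inference when the adjacent sentence uses the other term.

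There are also backstops. Table 8 still applies if the 500 msec hold is not met, ECG abnormalities can be recorded as adverse events, high-risk participants have ECGs every cycle, Section 8.3.3 refers sites to the lenvatinib prescribing information, and the investigator may stop treatment. These reduce the risk. However, Section 6.6.2 sends sites to the specific subsections before Table 8, so the ambiguous rule is read first. The documents do not reproduce the CTCAE grades for QT, so whether Table 8 closes the gap cannot be settled from them.

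Two further points are fair. The restart at a lower dose is worded as guidance, and a reduction made through misreading may qualify for the error exception with Sponsor approval. And the note to exclusion criterion 8, "Medically controlled arrhythmia would be permitted", says nothing about slow rates, so it is weak evidence that such participants will enrol; the list in Section 8.3.3 is better evidence.

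**Conclusion.** The inconsistency is real. As written, the hold is on uncorrected QT and the resume is on QTc. Applied literally, the hold comes 26 msec late on the QTcF scale at 70 bpm and 50 msec late at 80 bpm. Below about 53 bpm it can fire with QTcF already under the resume limit. Within 57 to 63 bpm the wording hardly matters.

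These are conversions between two measures at assumed heart rates. They are not an error rate: the documents give no heart rates, no frequency of QT events and no indication of how sites read the rule. The practical effect depends on a site taking the sentence literally, which is probably uncommon. This is a minor safety-wording defect that should be corrected. It has no bearing on the response rate, the sample size or any efficacy analysis.

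**What to change.** Reword the two sentences of Section 6.6.2.10 along these lines: *Withhold lenvatinib if QTcF is >500 msec. Resume at a reduced dose once QTcF is <480 msec or has returned to baseline.* Both thresholds stay as they are. Naming QTcF in the hold sentence closes the gap; naming it in the resume sentence makes explicit what Section 8.3.3 already implies. The rewording also states 500 msec as an absolute value, so it cannot be taken as a change from baseline.

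The cost is two sentences. No new measurements are needed because Section 8.3.3 already requires QTcF. The change can go into the next amendment as a minor correction, without a separate letter to sites or urgent action.

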6.6.2.11 Management of Osteonecrosis of the Jaw

Perform an oral examination prior to treatment with lenvatinib and periodically during lenvatinib treatment. Advise participants regarding good oral hygiene practices. Avoid invasive dental procedures, if possible, while on lenvatinib treatment, particularly in participants at higher risk. For participants requiring invasive dental procedures, discontinuation of bisphosphonate treatment may reduce the risk of ONJ. Withhold lenvatinib if ONJ develops and restart based on clinical judgement of adequate resolution (see Section 6.6.4).

6.6.3 Dose Modifications for Overlapping Toxicities

Based on the known toxicity profiles of pembrolizumab and lenvatinib, certain treatment-related AEs are uniquely associated with one drug versus the other. For example, hypertension, arterial thrombotic events, proteinuria, and hemorrhagic events are known risks for lenvatinib treatment, while immune-related AEs are risks for pembrolizumab treatment. However, certain AEs, such as such as diarrhea, hypothyroidism, and liver enzyme elevation, may be initially considered attributable to either study drug. Therefore, evaluation of attribution is important for determining the study drug most likely related to the AE, or an alternative etiology, and subsequently proper clinical management. The following aspects should be considered:

1. Timing of AE onset

Since lenvatinib is dosed daily and continuously due to a relatively short half-life (28 hours), and pembrolizumab is dosed Q6W due to a long half-life, lenvatinib can be interrupted to assess whether an AE improves/resolves with dechallenge (ie, interruption of treatment) based on the following 2 scenarios:

- If an AE is identified during a treatment cycle (ie, between 2 pembrolizumab doses), only lenvatinib dose interruption is needed.
- If an AE is identified at the beginning of a treatment cycle, lenvatinib can be interrupted and dosing of pembrolizumab should be held.

If the participant recovers from an AE in response to lenvatinib interruption (ie, positive dechallenge), the event is more likely to be related to lenvatinib. Otherwise, after excluding other alternative explanations, an irAE should be considered.

2. Severity of AE

If an AE is suspected to be treatment-related and is severe/life-threatening at the time of onset or is rapidly worsened, action including interrupting both drugs and initiating treatment with a corticosteroid (with exception of hypothyroidism, T1DM) and other supportive care should be taken promptly.

3. Participants receiving the combination therapy (pembrolizumab + lenvatinib) must discontinue study therapy if any of the following occur:

- ALT or AST $>5 \times$ ULN for more than 2 weeks.
Pembrolizumab will have already been permanently discontinued per [Table 6](#) but lenvatinib may be administered at a reduced dose by the time this criterion is met and must be permanently discontinued immediately.
- ALT or AST $>3 \times$ ULN and (TBL $>2 \times$ ULN or INR >1.5).
Although [Table 6](#) advises pembrolizumab to be withheld (interrupted), and [Table 8](#) advises lenvatinib to have no dose modification or a reduction, if this criterion is met, both drugs must be permanently discontinued immediately.

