12. Have adequate organ function as defined in the following table ([Table 4](#)). Specimens must be collected within 10 days prior to the start of study intervention.

Table 4 Adequate Organ Function Laboratory Values

System	Laboratory Value
Hematological	
Absolute neutrophil count (ANC)	$\geq 1500/\mu\text{L}$
Platelets	$\geq 100\,000/\mu\text{L}$
Hemoglobin	$\geq 9.0\text{ g/dL}$ or $\geq 5.6\text{ mmol/L}^a$
Renal	
Creatinine AND ^b /OR Measured or calculated ^c creatinine clearance (GFR can also be used in place of creatinine or CrCl)	$\leq 1.5 \times \text{ULN}$ AND ^b /OR $\geq 30\text{ mL/min}$ for participant with creatinine levels $> 1.5 \times \text{institutional ULN}$
Hepatic	
Total bilirubin	$\leq 1.5 \times \text{ULN}$ OR direct bilirubin $\leq \text{ULN}$ for participants with total bilirubin levels $> 1.5 \times \text{ULN}$
AST (SGOT) and ALT (SGPT)	$\leq 2.5 \times \text{ULN}$ ($\leq 5 \times \text{ULN}$ for participants with liver metastases)
Coagulation	
International normalized ratio (INR) OR prothrombin time (PT) Activated partial thromboplastin time (aPTT)	$\leq 1.5 \times \text{ULN}$ unless participant is receiving anticoagulant therapy as long as PT or PTT is within therapeutic range of intended use of anticoagulants
ALT (SGPT)=alanine aminotransferase (serum glutamic-pyruvic transaminase); AST (SGOT)=aspartate aminotransferase (serum glutamic-oxaloacetic transaminase); CrCl=creatinine clearance; GFR=glomerular filtration rate; ULN=upper limit of normal. ^a Criteria must be met without erythropoietin dependency and without packed red blood cell (pRBC) transfusion within last 2 weeks. ^b Applicable only when local guidelines require both assessments. ^c CrCl should be calculated per institutional standard. Note: This table includes eligibility-defining laboratory value requirements for treatment; laboratory value requirements should be adapted according to local regulations and guidelines for the administration of specific chemotherapies.	

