All Other irAEs	Persistent Grade 2	Withhold	
Based on severity of AE administer corticosteroids	
Ensure adequate evaluation to confirm etiology or exclude other causes
	Grade 3	Withhold or discontinue based on the event ^e		
	Recurrent Grade 3 or Grade 4	Permanently discontinue		
AE(s)=adverse event(s); ALT=alanine aminotransferase; AST=aspartate aminotransferase; CTCAE=Common Terminology Criteria for Adverse Events; DRESS=Drug Rash with Eosinophilia and Systemic Symptom; GI=gastrointestinal; IO=immuno-oncology; ir=immune-related; IV=intravenous; SJS=Stevens-Johnson Syndrome; T1DM=type 1 diabetes mellitus; TEN=Toxic Epidermal Necrolysis; ULN=upper limit of normal. Note: Non-irAE will be managed as appropriate, following clinical practice recommendations. ^a AST/ALT: >3.0 to 5.0 × ULN if baseline normal; >3.0 to 5.0 × baseline, if baseline abnormal; bilirubin:>1.5 to 3.0 × ULN if baseline normal; >1.5 to 3.0 × baseline if baseline abnormal ^b AST/ALT: >5.0 to 20.0 × ULN, if baseline normal; >5.0 to 20.0 × baseline, if baseline abnormal; bilirubin:>3.0 to 10.0 × ULN if baseline normal; >3.0 to 10.0 × baseline if baseline abnormal ^c AST/ALT: >20.0 × ULN, if baseline normal; >20.0 × baseline, if baseline abnormal; bilirubin: >10.0 × ULN if baseline normal; >10.0 × baseline if baseline abnormal ^d The decision to withhold or permanently discontinue pembrolizumab monotherapy, coformulations or IO combinations is at the discretion of the investigator or treating physician. If control achieved or ≤ Grade 2, pembrolizumab monotherapy, coformulations or IO combinations may be resumed. ^e Events that require discontinuation include, but are not limited to: encephalitis and other clinically important irAEs (eg, vasculitis and sclerosing cholangitis).				

Dose Modification and Toxicity Management of Infusion Reactions Related to Pembrolizumab

Pembrolizumab may cause severe or life-threatening infusion reactions including severe hypersensitivity or anaphylaxis. Signs and symptoms usually develop during or shortly after drug infusion and generally resolve completely within 24 hours of completion of infusion. Dose modification and toxicity management guidelines on pembrolizumab associated infusion reaction are provided in [Table 7](#).

Table 7 Pembrolizumab Infusion Reaction Dose Modification and Treatment Guidelines

NCI CTCAE Grade	Treatment	Premedication at Subsequent Dosing

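### The mandatory liver stop in Section 6.6.3 item 3 is not reconciled with Table 4's entry limits or with Table 6's baseline-adjusted grading

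*Combined protocol and SAP*

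**What the plan says.** Section 6.6.3 item 3 applies to participants receiving the combination and requires them to discontinue study therapy if either of two criteria occurs.

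- Criterion 1 is "ALT or AST $>5 \times$ ULN for more than 2 weeks". The explanatory text says "Pembrolizumab will have already been permanently discontinued per" Table 6, and that "lenvatinib may be administered at a reduced dose by the time this criterion is met and must be permanently discontinued immediately".
- Criterion 2 is ALT or AST above 3×ULN together with total bilirubin above 2×ULN or INR above 1.5. The explanatory text notes that Tables 6 and 8 advise less, and then says "if this criterion is met, both drugs must be permanently discontinued immediately".

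Table 4 (Section 5.1) allows entry with AST/ALT up to 2.5×ULN, or up to 5×ULN with liver metastases. Total bilirubin may exceed 1.5×ULN, with no stated upper limit, if direct bilirubin is within normal limits. The coagulation limit is 1.5×ULN, "unless participant is receiving anticoagulant therapy as long as PT or PTT is within therapeutic range of intended use of anticoagulants".

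Table 6 (Section 6.6.1) withholds pembrolizumab for Grade 2 AST/ALT elevation and stops it permanently for Grade 3 or 4. Footnote b defines Grade 3 as "AST/ALT: >5.0 to 20.0 × ULN, if baseline normal; >5.0 to 20.0 × baseline, if baseline abnormal". Footnote a defines Grade 2 in the same two ways, from 3.0 to 5.0.

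For Grade 3 or intolerable Grade 2 toxicity, Table 8 (Section 6.6.2) says "Interrupt lenvatinib until resolved to Grade 0-1, or tolerable Grade 2", followed by a dose-level reduction.

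**The concern.** Item 3 is mandatory and ends treatment with both drugs, so it should agree with the tables that decide who enters and how liver values are graded. It departs from them in two ways.

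First, Table 4 makes deliberate allowances for liver metastases, for anticoagulation and for raised total bilirubin with normal direct bilirubin. Criterion 2 carries none of these allowances. It also uses an absolute INR where Table 4 uses a multiple of ULN. Some participants can therefore be eligible with values that already satisfy it. Section 6.6.5 applies the inclusion criteria again before Second Course treatment, so the mismatch recurs there.

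Second, the text under criterion 1 assumes that Table 6 has already dealt with pembrolizumab. If it has not, a site following the explanatory sentence would stop lenvatinib only, while a site following the lead-in would stop both.

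The stakes are consistent handling of liver toxicity across sites and a consistent count of discontinuations due to AEs, which is a secondary safety endpoint (Section 3). No effect on the ORR estimate is claimed.

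**Working it through.** There is no planned figure to reproduce. The check sets the thresholds side by side. ALT/AST and bilirubin are in multiples of ULN, and INR is absolute.

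**1. Table 4 against criterion 2.** Without liver metastases ALT/AST is capped at 2.5, which is below 3, so criterion 2 cannot be met at entry. With liver metastases the range >3 to 5 is admitted. The profiles below are illustrative:

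| Liver metastases | ALT | Total bilirubin | INR | Eligible under Table 4 | Meets criterion 2 |
|---|---|---|---|---|---|
| No | 2.5 | 2.5, direct normal | 2.5, anticoagulated | Yes | No |
| Yes | 4 | 1.5 | 1.5 | Yes | No |
| Yes | 4 | 2.5, direct normal | 1.0 | Yes | **Yes** |
| Yes | 4 | 1.0 | 2.5, anticoagulated | Yes | **Yes** |
| Yes | 4 | 1.0 | 1.6, not anticoagulated | Yes, if INR ULN is 1.1 | **Yes** |

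The last row depends on the laboratory's INR ULN, which the documents do not give. For an assumed ULN of 1.0, 1.1, 1.2 or 1.3, Table 4 allows INR up to 1.5 × ULN = 1.50, 1.65, 1.80 or 1.95. Only at ULN 1.0 does this route close.

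**2. Table 4 against criterion 1.** The highest eligible ALT/AST is 5, and the criterion needs more than 5 for over two weeks. Nobody meets it on eligibility values.

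**3. Table 6 against the statement under criterion 1.** Let b be baseline ALT/AST. If b is normal, Table 6 withholds above 3 and discontinues above 5. If b is abnormal, it withholds above 3b and discontinues above 5b. For an on-study value of 5.1:

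| b | Withhold above (3b) | Discontinue above (5b) | 5.1 / b | What Table 6 asks at 5.1 |
|---|---|---|---|---|
| 1.0 (normal) | 3 | 5 | 5.10 | Discontinue |
| 1.1 | 3.3 | 5.5 | 4.64 | Withhold |
| 1.5 | 4.5 | 7.5 | 3.40 | Withhold |
| 2.5 | 7.5 | 12.5 | 2.04 | Neither |
| 4 | 12 | 20 | 1.27 | Neither |
| 5 | 15 | 25 | 1.02 | Neither |

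So for any abnormal baseline, values above 5 and up to 5b can meet criterion 1 although Table 6 has not required permanent discontinuation. A baseline of 2.5 is eligible without liver metastases, so this problem is not confined to that subgroup.

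**4. Which drug stops.** Under criterion 1 the lead-in says to discontinue study therapy, but the explanatory text directs only lenvatinib to stop. Under criterion 2 the explanatory text names both drugs. Only criterion 1 relies on Table 6 having acted first.

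**5. Table 8 (minor).** With a normal baseline, ALT/AST above 5 falls in the Grade 3 band of Table 6's footnote. Table 8 interrupts lenvatinib for Grade 3 until resolution, while the text under criterion 1 pictures it continuing at a reduced dose.

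**The case against.** The strongest reply is that Section 6.6.3 is meant to govern. Sections 6.6 and 6.6.2 both send overlapping toxicities there, and liver enzyme elevation is named as one. For criterion 2 the section acknowledges that Tables 6 and 8 advise less and overrides them. An absolute safety rule placed over baseline-adjusted tables is a legitimate clinical choice. For criterion 1 the lead-in already stops study therapy, so the sentence about Table 6 is only explanatory.

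Much of this stands. Between criterion 2 and Tables 6 and 8 there is a stated override, not a contradiction. It does not mention Table 4, however, and it does not cover criterion 1. There the inaccurate sentence is the reason why only lenvatinib is named.

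A reader might also infer that eligible participants trigger a stop before their first dose because of Tables 4, 6 and 8 together. The documents do not support that. The entry-value problem comes only from Table 4 against criterion 2, and item 3 covers participants receiving the combination, so it would operate from the start of treatment. Section 10.3.2 does not count day-to-day fluctuation of a non-worsening pre-existing condition as an AE, and exclusion criterion 27 lets the investigator exclude for a laboratory abnormality. These may keep some cases out, but neither tells a site how item 3 treats values that were abnormal at entry.

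On Table 8, the wording about lenvatinib is permissive. Footnote e also lets continuation be discussed with the Sponsor for asymptomatic laboratory abnormalities that are not clinically relevant. That point is therefore minor.

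**Conclusion.** Two inconsistencies hold on the text. (a) Table 4 admits a narrow group whose entry values already satisfy criterion 2. They have liver metastases and ALT/AST >3 to 5×ULN, plus either total bilirubin >2×ULN with normal direct bilirubin, or INR >1.5 under therapeutic anticoagulation or within 1.5×ULN. As written, the permanent stop would apply as soon as they receive treatment. (b) Where baseline ALT/AST is abnormal, criterion 1 can be met without Table 6 having stopped pembrolizumab, and the lead-in and explanatory text then differ on which drugs stop.

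The number affected cannot be estimated. The documents give neither the proportion with liver metastases nor the distribution of baseline ALT/AST. It is probably small for (a), which needs two abnormalities together. A reader might take an assumed liver-metastasis rate as the size of the group, or treat every participant starting above 3×ULN as a mandatory stop. Neither follows: ALT/AST >3×ULN alone triggers nothing in item 3, and (b) depends on any abnormal baseline, with or without metastases.

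The point deserves correction because the text is mandatory and the stop is permanent, not because a large number of participants is shown to be affected. The only outside assumption is the INR ULN of 1.0 to 1.3, and it bears on one of the three entry profiles.

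**What to change.** Reconcile Section 6.6.3 item 3 with Tables 4, 6 and 8:

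- State how the criteria apply to participants whose ALT/AST, total bilirubin or INR is already abnormal at entry, including at Second Course entry. Cover therapeutic anticoagulation and raised total bilirubin with normal direct bilirubin.
- Express INR on the same scale in Table 4 and Section 6.6.3.
- Correct the statement that Table 6 will already have stopped pembrolizumab, and make the explanatory text under criterion 1 agree with the lead-in on which drugs stop.
- Align the remark about reduced-dose lenvatinib with Table 8.

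The clinical team chooses the reference (ULN or baseline) and the thresholds; none is proposed here. The cost is a protocol clarification, with no new data and no added participants.
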